4 PATIENT POPULATION

4.1 Inclusion Criteria

1. Patient is at least 20 years of age
2. Patient must be willing and capable of giving written Informed Consent, adhering to dosing and visit schedules, and meeting all study requirements
3. **Phase 2:** If an archival tissue sample is not available, a tumor biopsy will be required.
4. Previously treated patient with histologically or cytologically confirmed (archival tissue accepted) locally advanced or metastatic non-small cell lung cancer (NSCLC) and is not a candidate for definitive therapy
 - **Phase 1:** No test for mutational status is required
 - **Phase 2:** Documented EGFR or HER2 exon 20 insertion mutation (including duplication mutations) in NSCLC patients. Patients will be enrolled based on documentation of mutational status using PCR or a validated next generation sequencing detection analysis test.
 - Documented *EGFR* exon 20 insertion mutation, including D770_N771insSVD, D770_N771insNPG, V769_D770insASV, H773_V774insNPH, or any other *EGFR* exon 20 in-frame insertion mutation (including duplications).
 - Documented *HER2* exon 20 insertion mutation, including A775_G776insYVMA, G776_V777insVC, or P780_Y781insGSP, or any other *HER2* exon 20 in-frame insertion mutation (including duplications).
5. Patient has measurable NSCLC disease, as per the Response Evaluation Criteria in Solid Tumors (RECIST, version 1.1). Metastatic lesions in bone, CNS, or in brain cannot be used for target lesions.
6. Prior treatment status:
 - **Phase 1:** Patient with refractory NSCLC to available standard therapies
 - **Phase 2:** Progression after at least one systemic therapy for locally advanced or metastatic disease
7. Patient has an Eastern Cooperative Oncology Group (ECOG) performance status 0 or 1

8. Patient has recovered from prior systemic therapy for metastatic disease to Grade ≤ 1 for non-hematologic toxicities (except for Grade ≤ 2 peripheral neuropathy) and has adequate hematologic, hepatic, and renal function at Baseline, as defined by:
 - Leukocytes $\geq 3.0 \times 10^9/L$
 - Absolute neutrophil count (ANC) must be $\geq 1.5 \times 10^9/L$
 - Platelet count $\geq 100 \times 10^9/L$
 - Hemoglobin $\geq 9.0 \text{ g/dL}$
 - Total bilirubin $\leq 2 \text{ mg/dL}$; if hepatic metastases are present, $\leq 2.5 \times \text{ULN}$
 - SGOT (AST) and SGPT (ALT) $\leq 2.5 \times \text{ULN}$ with the following exception; Patients with liver metastases AST, ALT $\leq 5 \times \text{ULN}$

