4.2 Exclusion Criteria

1. **Phase 2 :** Patient has EGFR T790M mutation or any other acquired EGFR exon 20 point mutation
2. **Phase 2 :** Patient has had previous treatment with poziotinib. The currently approved TKIs that are not considered to be exon 20 insertion-selective are permissible.
3. Patient is concurrently receiving chemotherapy, biologics, immunotherapy for cancer treatment; systemic anti-cancer treatment or investigational treatment should not be used within 2 weeks prior to Cycle 1, Day 1; local radiation therapy for bone pain may be allowed.
4. Patient has used strong inhibitors/inducers of CYP3A4 and CYP2D6 within 1 month prior to Cycle 1, Day 1.
5. Patient has brain metastases and is clinically symptomatic, requires high dose or increasing doses of systemic corticosteroids, or needs any anticonvulsant therapy for metastatic brain disease.
6. Patient has a high risk for or history of congestive heart failure (CHF) Class III/IV according to the New York Heart Association (NYHA) Functional Classification or serious cardiac arrhythmias requiring treatment. Cardiac ejection fraction $<50\%$ as determined by either echocardiogram (ECHO) or multi-gated acquisition (MUGA) during Screening.

7. Patient has had another primary malignancy within 3 years prior to starting study treatment, except for adequately treated basal or squamous cell carcinoma of the skin or cancer of the cervix in situ
8. Patient is confirmed to have clinically significant or recent acute gastrointestinal disease presenting as diarrhea and/or coloenteritis as a main symptom (ie, acute enteritis, malabsorption, or Common Terminology Criteria for Adverse Events (CTCAE, version 5.0) Grade 2 or above diarrhea due to other etiologies)
9. Patient has an active Grade ≥ 2 skin disorder, rash, mucositis, or skin infection that needs medication or therapy or existing Grade ≥ 2 skin toxicity from previous therapies; Grade > 2 neuropathy, Grade ≥ 2 pneumonitis.
10. Patient is unable to take drugs orally due to disorders or diseases that may affect gastrointestinal function, such as inflammatory bowel diseases (eg, Crohn's disease, ulcerative colitis) or malabsorption syndrome, or procedures that may affect gastrointestinal function, such as gastrectomy, enterectomy, or colectomy

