5.3 Timing of Assessments and Procedures

5.3.1 Screening Visit

Informed Consent must be obtained prior to any study procedures. The following assessments should be performed at the Screening Visit within 30 days of Day 1.

- Verify existing pathology and tissue-based mutation diagnostic records, and available imaging test reports from medical records before consenting the patient. Tumor assessment scans for eligibility assessment must be completed within 4 weeks of Cycle 1, Day 1.
- Informed Consent
- Patient ID
- Relevant medical history
- Demographic data
- Height and weight
- Complete physical examination, including auscultation
- Vital signs
- Resting O₂ saturation
- Pulmonary function assessment (Chest X-ray and pulmonary function test)
- Eastern Cooperative Oncology Group (ECOG) Performance Status assessment
- Pregnancy test (beta human chorionic gonadotropin [β -HCG]) in women of childbearing potential
- Hepatitis B tests (surface antigen, core antibody, and surface antibody)
- Hepatitis C antibody test
- HIV antibody test
- Screening/Baseline tumor assessment within 4 weeks prior to **Cycle 1, Day 1**
- Baseline brain MRI scan for patients with known brain metastases (if needed)
- Tissue and whole blood collection
 - Phase 2 only: Tissue sample (archival sample or tissue biopsy) for genotyping
 - Phase 2 only: Whole blood sample for plasma circulating tumor DNA (ctDNA) analysis
 - All patients: Whole blood sample for CYP2D6 genotyping (metabolic profile analysis)
- Complete blood count (CBC) with 5-part differential and platelets prior to pozotinib administration (may be obtained up to 14 days prior to **Cycle 1, Day 1**)
- Serum chemistry, including KL-6 and C-reactive protein (may be obtained up to 14 days prior to **Cycle 1, Day 1**)

- 12-lead electrocardiogram (ECG)
- Echocardiogram or MUGA scan to evaluate cardiac ejection fraction (ECHO or MUGA results within 6 months prior to Cycle 1, Day 1 is acceptable if there is no major known cardiac event during this period)
- Adverse event assessment using NCI CTCAE, version 5.0, record SAEs before the first dose of pozotinib
- Concomitant medications

5.3.2 Treatment Period – Cycle 1, Day 1

- Eligibility confirmation
- Admission to hospital (**Phase 1 – Dose-Finding only**)
- Weight
- Physical examination
- Vital signs
- Resting O₂ saturation
- Pulmonary function assessment (if not evaluated within the past 6 months)
- ECOG Performance Status assessment

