5.4.6 Tumor Assessment

Results of standard-of-care tests or examinations performed within 28 days prior to Cycle 1, Day 1 may be used for the Screening/Baseline tumor assessment. Tumor assessments must be performed using computed tomography (CT), positron emission tomography (PET)/CT, or magnetic resonance imaging (MRI). The image will be reviewed by a local radiologist as the Baseline image for response assessment and per the Investigator's standard of care.

For patients with known brain metastases, a Baseline brain MRI scan (within 28 weeks prior to Cycle 1, Day 1) will also be performed to assess the status of brain metastases if present.

Tumor assessments will also be performed at 4 weeks (Cycle 2, Day 1 [up to Cycle 2, Day 10]), 8 weeks (Cycle 3, Day 1 [up to Cycle 3, Day 10, with at least 28 days from previous tumor assessment]), and then every 8 weeks (\pm 10 days) for up to 24 months or until disease progression, death, intolerable adverse events (AEs), or other protocol-specified reasons for patient withdrawal or for a maximum of 24 months.

Tumor assessment will be performed at the Safety Follow up Visit unless the patient has documented disease progression or has undergone a tumor assessment within the previous 8 weeks.

Each subsequent tumor assessment must use the same baseline radiographic technique, either CT, PET/CT, or MRI. Tumor assessments will be made according to RECIST criteria, Version 1.1 [\[22\]](#) using appropriate radiographic imaging or other techniques. For radiographic assessment, CT, PET/CT, or MRI must be performed at every assessment. Patient enrollment and clinical decisions will be based on local review.

Measurable and non-measurable lesions that will not be followed by radiographic methods should be documented appropriately.

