8.5 Efficacy Analyses

Phase 1: No efficacy analyses will be performed in Phase 1.

Phase 2: The primary efficacy variables, as described below, will be summarized and analyzed descriptively, along with 95% CI, for each cohort based on local radiographic review.

- **Objective Response Rate (ORR)** will be assessed according to the Response Evaluation Criteria in Solid Tumors (RECIST) Guidelines, version 1.1 [22] and is defined as the best response [Complete Response (CR) + Partial Response (PR)] recorded from the start of the study until the end of study in patients who received at least 1 dose of pozotinib. The ORR will be based on the Evaluable Population.

The primary endpoint analysis will be performed using point estimate and the 95% CI.

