e) Resting O₂ saturation and will be assessed at Screening, Cycle 1, Days 1, 8, and 15, Day 1 of each subsequent cycle, and at the Safety Follow-up Visit.

f) Routine monitoring for evidence of interstitial lung disease (ILD) will be done at Screening, on Day of Cycles 1-3, every 8 weeks thereafter, and at the Safety Follow up Visit. In addition, it will be assessed on Days 8 and 15 of Cycle 1.

g) The patient's ECOG score will be evaluated at Screening, Cycle 1, Days 1, 8, and 15, Day 1 of each subsequent cycle, and at the Safety Follow-up Visit.

h) A urine or plasma pregnancy test (β-hCG), in women of child-bearing potential, is required at Screening, Day 1 of each cycle, and at the Safety Follow-up. A urine sample is only needed if a urine pregnancy test is done.

i) Tests will be for hepatitis B surface antigens and hepatitis B core and surface antibodies. If the hepatitis B surface antigen test is positive, the patient will be excluded from the study. If only the hepatitis B core antibody and/or hepatitis B surface antibody are positive, a serum hepatitis HBV DNA test will be done. If this test is positive the patient will be excluded from the study.

j) If the hepatitis C antibody test is positive, an HCV RNA test will be done. If this test is positive the patient will be excluded from the study.

k) Whole blood samples will be used for the HIV test. If this test is positive, the patient will be excluded from the study.

l) The Screening/Baseline tumor assessment will be performed within 28 days prior to, or on Cycle 1, Day 1, and additional assessments will be made at 4 weeks (Cycle 2, Day 1 [up to Cycle 2, Day 10]), at 8 weeks (Cycle 3, Day 1 [up to Cycle 3, Day 10, with at least 28 days from previous tumor assessment]), and then every 8 weeks (±10 days) thereafter for up to 24 months. Assessment is also done at Safety Follow-up visit unless disease progression is documented or assessment has been done within 2 months of Safety-follow up visit.

m) If an archival tissue sample is not available, a tumor biopsy will be required. A tumor genotyping report is required to confirm patient mutation eligibility. Collecting a tissue sample at progression is optional but is highly encouraged. Tumor tissue FFPE samples will be stored at room temperature.

n) Whole blood samples (4 mL) will be drawn at Screening for CYP2D6 metabolic profile testing.

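### In Phase 2 the baseline scan may predate the last doses of prior systemic therapy, so tumor change from that therapy can enter ORR, DCR and PFS, in either direction

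*Combined protocol and SAP*

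**What the plan says.** **Scan window.** Section 5.4.6 allows existing routine imaging as baseline: "Results of standard-of-care tests or examinations performed within 28 days prior to Cycle 1, Day 1 may be used for the Screening/Baseline tumor assessment". Section 5.3.1 gives the same limit for eligibility scans: "Tumor assessment scans for eligibility assessment must be completed within 4 weeks of Cycle 1, Day 1". Footnote l of the Phase 2 schedule (Appendix 2) reads: "The Screening/Baseline tumor assessment will be performed within 28 days prior to, or on Cycle 1, Day 1". Section 5.3.1 also has sites check available imaging reports before consent, so reuse of routine scans is foreseeable.

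**Washout.** Exclusion criterion 3 in Section 4.2: "systemic anti-cancer treatment or investigational treatment should not be used within 2 weeks prior to Cycle 1, Day 1".

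**Prior progression.** For Phase 2, inclusion criterion 6 in Section 4.1 asks for: "Progression after at least one systemic therapy for locally advanced or metastatic disease". It does not say that the progression must be on the latest regimen, or visible on the baseline scan.

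**Oversight.** Under Section 5.1, routine results obtained before consent need sponsor approval and discussion with the Medical Monitor. Under Section 5.2, the sponsor or CRO confirms eligibility. Neither section mentions the scan date relative to the last prior dose.

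**Endpoint.** Section 8.5 defines ORR as the best CR or PR "recorded from the start of the study until the end of study in patients who received at least 1 dose of pozotinib", by local review under RECIST 1.1. It plans no efficacy analysis in Phase 1.

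**The concern.** The scan window is twice as long as the washout. A patient could have a routine scan on Day -28, stay on chemotherapy, immunotherapy or a TKI until about Day -15, and start study drug on Day 1 with every stated timing rule met. The baseline would then precede the last doses of the earlier treatment.

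The progression criterion does not exclude this. A patient who progressed on a first line, and then stopped a second line for another reason while stable or shrinking, still qualifies. Further shrinkage from the second line would be measured from the study baseline.

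The opposite case is equally possible. If the last regimen was failing, growth between an old scan and Day 1 counts against study drug and can hide a response or bring forward RECIST progression.

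Phase 2 has no control arm in which such effects would also appear. ORR and DCR use the baseline directly, and PFS uses it through RECIST progression. The first on-treatment scan is at Week 4. With a scan 28 days before Day 1 and another 28 days after it, 28/56, or half, of the measured interval precedes study drug.

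**Working it through.** **1. The plan's own precision figure.** Section 8.1 gives a 95% CI width of 0.424 for 20 patients at an expected ORR of 30%. The exact (Clopper-Pearson) interval for 6/20 is 0.1189 to 0.5428, width 0.4239, which rounds to 0.424. The figure reproduces. This point changes neither it nor the sample size.

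**2. The overlap.**
- Scan look-back: 28 days (Sections 5.3.1 and 5.4.6; Appendix 2, footnote l).
- Washout: 2 weeks = 14 days (Section 4.2).
- Prior dosing that may follow the baseline scan: 28 - 14 = up to about 14 days.
- If the scan had to follow the last prior dose: 0 days.

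**3. Radiotherapy.** Section 4.2 says "local radiation therapy for bone pain may be allowed", without a washout. But Section 4.1 says "Metastatic lesions in bone, CNS, or in brain cannot be used for target lesions", so irradiated bone lesions cannot supply target-lesion shrinkage. The gap concerns systemic therapy.

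**4. Effect of one misclassified response.** 1/20 = 5 points, and slightly more if fewer than 20 patients are evaluable.

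| Responders of 20 | ORR | Exact 95% CI |
|---|---|---|
| 5 | 25% | 8.7% to 49.1% |
| 6 | 30% | 11.9% to 54.3% |
| 7 | 35% | 15.4% to 59.2% |

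**5. Illustration of the upward case.** The documents give no inputs, so both of these are assumptions:
- f, the share of patients scanned before their last prior dose and not progressing on that regimen: 5% to 30%.
- c, the share of those who would reach PR from carry-over alone: 10% to 25%.

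With true ORR p, expected observed ORR = p + (1 - p) × f × c.

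- p = 30%, low: 0.30 + 0.70 × 0.05 × 0.10 = 30.4% (0.07 extra responders per 20).
- p = 30%, high: 0.30 + 0.70 × 0.30 × 0.25 = 35.3% (1.05 per 20).
- p = 17%, low: 0.17 + 0.83 × 0.05 × 0.10 = 17.4% (0.08 per 20).
- p = 17%, high: 0.17 + 0.83 × 0.30 × 0.25 = 23.2% (1.25 per 20).

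The expected upward shift is thus about 0.4 to 6 points under these assumptions. The downward case would offset some or all of it, by an amount the documents do not let one estimate.

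**The case against.** **Oversight exists.** A site cannot use a pre-consent routine scan on its own authority (Section 5.1), and eligibility is confirmed centrally (Section 5.2). This stands as a partial control. But no criterion directs either review to the last prior dose, so an approved scan can still fall before it.

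**The upward case is narrow.** It needs a patient who progressed earlier, was benefiting from a later agent, and stopped it about two weeks before Day 1. If the reason was intolerance, Section 4.1 (criterion 8) also requires recovery of non-hematologic toxicity to Grade 1 or less, apart from neuropathy, and Section 4.2 (criterion 9) excludes existing Grade 2 or higher skin toxicity. The background sections report low activity of earlier TKIs: 5% and 8.7% response in EGFR exon 20 insertions, and 13% with dacomitinib in HER2-mutant disease. This largely stands and limits the likely size. It does not make carry-over negligible: Section 1.1.1.2 also reports partial responses in 3 of 8 HER2-mutant patients on afatinib and calls chemotherapy efficacy modest, which is not nil.

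**The bias may be conservative.** Where the last regimen had failed, an old baseline lowers ORR. That is correct, but the two errors need not cancel in a cohort of 20, and neither measures change on study drug.

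**The remedy is incomplete.** A scan the day after the last prior dose would comply, and later shrinkage from that dose would still be counted. This also stands: the rule removes prior dosing after baseline, not all carry-over.

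**Conclusion.** The gap is real in Phase 2. The documents permit up to about 14 days of prior systemic therapy after the baseline scan, and no eligibility, oversight or analysis rule prevents or examines this. Tumor change from the earlier regimen can enter ORR, DCR and PFS in either direction. Each misclassified response is worth 5 points in a cohort of 20. How many there would be cannot be derived from the documents, and the 0.4 to 6 point range for the upward case rests wholly on assumed inputs.

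Four stronger readings are tempting but unsupported:
- *That prior-therapy effect will be credited to study drug and ORR is inflated.* The text makes this possible, not certain, and downward bias is equally permitted.
- *That one or two affected patients of 20 mean a 5 to 10 point shift.* This would require every affected patient to become a false responder.
- *That this erodes the 13-point gap between 17% and 30%.* Section 8.1 gives those rates as the hypothesis of the global study SPI-POZ-202 and specifies no test here. The harm is to an estimate whose interval is already 42.4 points wide.
- *That Phase 1 results are affected.* Section 8.5 plans no efficacy analysis there.

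This is a worthwhile, inexpensive improvement to how the primary endpoint is measured. It does not invalidate the design.

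**What to change.** For Phase 2 only, amend Sections 5.3.1 and 5.4.6 and footnote l of the Phase 2 schedule (Appendix 2 and its copy in the synopsis). The baseline scan used for response should be taken within 28 days before, or on, Cycle 1 Day 1, and after the last dose of prior systemic anti-cancer therapy. The existing washout always leaves about 14 days for such a scan, within the 30-day screening period. The washout, treatment rules, sample size and CI width are unchanged.

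Where an earlier scan is used anyway, record the scan date and the last prior dose date in the CRF. Report a sensitivity analysis of ORR, by cohort, excluding those patients.

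The cost is one sentence by amendment, the two dates where an earlier scan is used, and a repeat or later scan for a few patients who already have a routine one. The rule does not remove carry-over from doses given shortly before a compliant scan.

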1.1.3.1 Summary of Clinical Efficacy

NOV120101-202 was a Phase 2, prospective, open-label, multicenter, exploratory study conducted in adult patients with Stage 3B or 4 NSCLC (including lung adenocarcinoma) with acquired resistance to first-generation EGFR TKIs (gefitinib or erlotinib). This study was conducted by Hanmi and National OncoVenture. Patients were not screened for EGFR or HER2 exon 20 mutations.

The primary study endpoint was Progression-free Survival (PFS). In addition, a number of secondary and exploratory endpoints were also assessed, including PFS rate at 16 weeks of treatment, Objective Response Rate (ORR), Disease Control Rate (DCR), overall survival (OS), time to progression (TTP), time to objective response, duration of objective response, duration of disease control, and change in quality of life: EQ visual analog scale (EQ VAS) and EQ-5D index to measure levels of mobility, self-care, activity, pain/discomfort, and anxiety/depression. Exploratory endpoints included a population PK profile and a subgroup analysis of genetic information confirmed from tumor tissue and blood samples. The primary and secondary endpoints of ORR and DCR are discussed in this section.

Pozotinib was administered orally at a dose of 16 mg/day once daily for 28-day (4-week) continuous cycles until the patient exhibited PD or intolerable AEs that led to drug discontinuation. The planned enrollment for this study was 40 patients. Tumor response was assessed periodically at protocol-designated times.

Forty patients were enrolled, and 39 patients were included in the Full Analysis Set and the Safety Analysis Set. One patient was not treated with pozotinib and was excluded from the analyses. The Per Protocol Analysis Set included 35 patients; 3 were excluded because of noncompliance with treatment, and 1 was excluded because of an inclusion criterion deviation. The majority of patients withdrew from the study due to PD or lack of efficacy (72.5%, 29/39) followed by withdrawal of consent (17.5%, 7/39), AEs (5%, 2/39), and other (2.5%, 1/39).

In the Full Analysis Set, the majority of patients had an event, 87.18% (34/39) versus 92.31% (36/39), after independent and Investigator review, respectively. Regardless of the censoring rule used, the number of events remained uniform. The median PFS was 2.70 months by independent

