Cohort 1 enrolled a total of 115 patients who received 16 mg/day of pozotinib. The Intent-to-Treat analysis showed that 17 patients had a response (by RECIST) and 62 patients had stable disease for a 68.7% disease control rate (DCR). The confirmed objective response rate (ORR) was 14.8% (95% CI; 8.9%-22.6%). The median duration of response was 7.4 months. The best change in target lesion dimensions from Baseline is presented in **Figure 9**. The safety profile was at the high end of expected toxicities but in-line as to type of AE with other second-generation EGFR tyrosine kinase inhibitors. Permanent drug discontinuation related to AEs was seen in only 10% of patients but temporary drug interruption was seen in 88% of patients and dose reduction was seen in 68% of patients as permitted by protocol.

Figure 9 Best Percent Change in Sum of Target Lesion Dimension from Baseline

This study is being conducted to evaluate the safety of pozotinib in Japanese patients, a dose-escalating study beginning at 8 mg pozotinib QD and 4 mg BID is being conducted. Pharmacokinetic modeling of the 8 mg BID and 16 mg QD doses (the highest potential doses in the study), shows that BID dosing decreases fluctuations (i.e., difference between peak and trough concentrations) compared to QD dosing with a lower C_{max} (Figure 10) and the predicted AUC is expected to be similar for equivalent total daily doses. In Study HM-PHI-101, the 8-mg QD dose was well-tolerated in Phase 1 patients. In addition, activity and safety of BID dosing with pozotinib has not been previously investigated.

Figure 10 Simulated Poziotinib Plasma Concentrations Following QD and BID Dosing

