5.3.9 Long-Term Follow-up – Every 3 Months

- After study drug discontinuation, patients will be contacted every 3 months, for up to 2 years after patient's first dose of pozotinib, for survival assessment.

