8.5.1 Secondary Endpoints

- **DCR**, including CR, PR, and Stable Disease (SD), will be assessed using RECIST, version 1.1 and defined as the proportion of subjects who achieve CR, PR, and SD by the best response from the first dose of pozotinib to the end of study.
- **DoR** will be measured from the date that measurement criteria are first met for CR or PR (whichever status is recorded first) until the first subsequent date that progressive disease or death is documented.
- **PFS** is defined as the number of days from the treatment start date to the date of documented disease progression or death due to any cause. Disease progression will be determined by RECIST Version 1.1.

DCR, DoR, and PFS will be analyzed using descriptive statistics, for each cohort, and with 95% CI for DCR and Kaplan-Meier plot for DoR and PFS.

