- u) Pozotinib will be dispensed on Day 1 of each cycle. Pozotinib should be taken with food and a glass of water (approximately 240 mL) at approximately the same time(s) each day.
- v) During the Screening Period, only SAEs will be recorded. All AEs will be collected from Cycle 1, Day 1 through the Safety Follow-up Visit.
- w) Concomitant medications will be collected at Day 1 of each cycle, Day 8 and Day 15 during Cycle 1, and at the Safety Follow-up Visit.
- x) Telephone contact will be made to collect AE and concomitant medication information from patients on Cycle 1, Day 22, every week in Cycle 2, and **Day 15 (± 2 days)** in each cycle thereafter. During the long-term follow-up patients will be contacted every 3 months to assess survival.

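### Scheduled tumor scans end when a patient stops for toxicity but later deaths still count as PFS and DoR events, which modestly overstates PFS; Section 5.4.6 and Phase 2 footnote l also disagree

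*Combined protocol and SAP*

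**What the plan says.** Three parts of the plan bear on this point.

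- **Scan schedule.** Section 5.4.6 sets scans at 4 weeks, 8 weeks and every 8 weeks after that, "until disease progression, death, intolerable adverse events (AEs), or other protocol-specified reasons for patient withdrawal or for a maximum of 24 months". It adds one possible late scan: "Tumor assessment will be performed at the Safety Follow up Visit unless the patient has documented disease progression", or has been scanned in the previous 8 weeks. That visit falls 35 (±5) days after the last dose. Footnote l of the Phase 2 schedule (Synopsis and Appendix 2) says only "and then every 8 weeks (±10 days) thereafter for up to 24 months". The clause ending scans for adverse events or withdrawal is in Section 5.4.6 and in Phase 1 footnote l, but not in Phase 2 footnote l.
- **Later follow-up.** Appendix 2 states: "During the long-term follow-up patients will be contacted every 3 months to assess survival". Section 5.3.9 sets the length: "for up to 2 years after patient's first dose of pozotinib, for survival assessment". Section 4.3 limits this contact to patients who have consented and ends it when consent is withdrawn. The Phase 2 table shows no imaging in this period.
- **Endpoints.** Section 8.5.1 has PFS "defined as the number of days from the treatment start date to the date of documented disease progression or death due to any cause". DoR likewise ends at progression or death. Neither definition has a censoring rule, a limit on missed scans or a rule for new anticancer therapy. Both endpoints are secondary, for Phase 2 only, and are shown as Kaplan-Meier plots per cohort. Section 8.4 leaves further detail to a SAP; the text supplied contains no such rule.

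**The concern.** After a toxicity stop, progression can no longer be seen but death can. Take a patient who stops at Month 2, progresses at Month 4 and dies at Month 14. The safety-visit scan, if done, comes at about Month 3 and shows nothing. By the definition in Section 8.5.1 this patient has a PFS of 14 months rather than 4.

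The error runs one way, since a missed progression followed by death can only move the event later. It arises in patients who could not tolerate the drug, so poor tolerability would make PFS look longer. The data also matter: a later SAP can add a censoring rule, but it cannot recover scans that were never entered in the database.

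**Working it through.** **The plan's own figure.** There is no precision target for PFS or DoR. The only one is the 95% confidence interval width of 0.424 for ORR in Section 8.1. The exact (Clopper-Pearson) interval for 6/20 is 0.1189 to 0.5428, width 0.4239, so that figure is reproduced. The present point does not touch it.

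**Inputs from the documents**
- True median PFS of 3.65 months: the higher investigator figure for NOV120101-202 (Section 1.1.3.1).
- Stopping without progression, lower source (Section 1.2, Cohort 1 of SPI-POZ-202): "Permanent drug discontinuation related to AEs was seen in only 10% of patients".
- Stopping without progression, second source (Section 1.1.3.1, NOV120101-202): "followed by withdrawal of consent (17.5%, 7/39), AEs (5%, 2/39), and other (2.5%, 1/39"). Adverse events plus other reasons give 5% + 2.5% = 7.5%. The 17.5% who withdrew consent are kept apart, because Section 4.3 ends their survival contact and their deaths cannot enter the analysis. (The printed percentages fit 40 enrolled patients rather than 39; the difference is immaterial here.)

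**Assumption not in the documents.** Median survival after progression of 6 to 10 months.

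**Model.** Exponential progression (rate λ), stopping (rate μ) and death after progression (rate δ). After a stop only death is observed, and patients alive count as event-free. Then

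S_obs(t) = e^(−λt) + λ·e^(−δt)·{[1 − e^(−(λ−δ)t)]/(λ−δ) − [1 − e^(−(λ+μ−δ)t)]/(λ+μ−δ)}

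with λ = ln 2/3.65 = 0.1899 per month. For 10% stopping before progression, μ = λ·0.10/0.90 = 0.0211. For a 6-month post-progression median, δ = ln 2/6 = 0.1155.

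At 12 months:
- true PFS = e^(−0.1899×12) = 0.102
- added term = 0.1899 × 0.25 × (7.94 − 7.14) = 0.038
- observed PFS = 0.102 + 0.038 = 0.140

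| Case | Median PFS, months | 12-month PFS |
|---|---|---|
| Progression fully observed | 3.65 | 10.2% |
| 10% stop, deaths counted | 3.81-3.82 | 14-15% |
| 7.5% stop, deaths counted; 17.5% withdraw consent, censored at the stop (simulation) | about 3.8 | 14-15% |

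The median shift of about 0.16 months is roughly 5 days. In a cohort of 20, the 12-month shift is (0.14 to 0.15 − 0.10) × 20, or about one patient.

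**Check with actual scan timing.** A second simulation placed scans at weeks 4 and 8 and then every 8 weeks, included the safety-visit scan, and ended follow-up at 24 months (true median 3.65 months, 10% stopping, post-progression median 6 or 12 months).
- With patients still alive kept event-free to 24 months, 12-month PFS went from 12.3% to 15.4%, or from 12.2% to 16.5%.
- With patients still alive censored at their last scan and deaths counted, it went to 14.1% or 14.0%.
- Late deaths were the PFS event in 5-7% of patients, about 1.0 to 1.4 per cohort of 20. Their event dates moved later by 4.5 to 5.9 months on average.
- The safety-visit scan found progression in about 2% of all patients and did not remove the bias.
- Over progression medians from 2.7 to 7.4 months, 10% stopping raised 12-month PFS by 1.6 to 5.2 points.
- Here the Kaplan-Meier median is a poor gauge, because it falls on scan dates. It stayed at 3.68 months (week 16) when the progression median was 2.7. At 3.65, which lies almost on week 16, it jumped to 5.04-5.52 months. Landmark PFS is the steadier measure.

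**Effect of a 16-week limit.** Censoring at the last scan when death came more than 16 weeks after it gave 12-month PFS of 11.9% and 12.0%, against 12.3% and 12.2% with full scanning. The model makes stopping independent of progression, which toxicity-related stopping need not be.

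**The case against.** The strongest reply is that censoring and missed-scan rules normally sit in a SAP, and Section 8.4 defers to one. That stands for the analysis rule: last-scan and death dates are already collected, so a rule for late deaths could still be written. It does not stand for the scans themselves.

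Second, the endpoints are descriptive, no hypothesis is tested, and 20 patients per cohort leave wide uncertainty: 2/20 has an exact interval of 1% to 32%. This stands, and limits the importance of the point.

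Third, Phase 2 footnote l could be read as requiring scans to 24 months whatever the reason for stopping. But Section 5.4.6 says otherwise and the Phase 2 table has no imaging in long-term follow-up. The two texts conflict, and sites could follow either.

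Two stronger readings are tempting.
- A reader might add all non-progression stops in NOV120101-202 (25%) and infer a median of about 4.2 months and a 12-month PFS of 20-23%. The documents do not support this: 17.5 of those 25 points are consent withdrawals, whose survival contact ends under Section 4.3.
- A reader might infer that every later death counts. Deaths are captured only up to 2 years from first dose, and only in patients who consented to and remain in follow-up.

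**Conclusion.** The point holds in a limited form. The scan rule in Section 5.4.6 combined with the definitions in Section 8.5.1 dates some PFS events too late, always in the drug's favour. With 7.5-10% stopping for adverse events or other non-consent reasons, the median moves from 3.65 to about 3.8 months and 12-month PFS from about 10% to 14-15%.

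This rests on an assumed post-progression median of 6-10 months, exponential times, and stopping that is independent of progression. The simple model also omits scan timing, and neither model removes patients who stop in Cycle 1, whom the Evaluable Population of Section 8.3 excludes.

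DoR is exposed to the same error in the same direction. Its size was not computed; at the expected ORR of 30% there would be about 6 responders per cohort. ORR is not affected by this mechanism. It is also too strong to say that censoring these patients would be informative: that is plausible when the stop is for toxicity, but nothing in the documents shows it. It is a reason to place the 16-week rule in a sensitivity analysis rather than make it the primary rule.

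**What to change.** 1. Reconcile Section 5.4.6 with footnote l of the Phase 2 schedule (Synopsis and Appendix 2), so that one scan rule applies. For Phase 2 patients who stop without progression, record tumor assessments done as routine care, and the start date of any new anticancer therapy, until progression, death, consent withdrawal or 24 months.
2. In Section 8.5.1, add two sensitivity analyses of PFS and DoR:
   - one that censors at the last adequate assessment when progression or death comes more than 16 weeks (two 8-week intervals) after it;
   - one that counts stopping for toxicity, or starting new therapy, as an event.

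The cost is data entry for a few patients per cohort (7.5-10% of 20 is 1.5 to 2) and two additional analyses. No mandatory procedure is added. Routine scans will be irregular, so the yield is uncertain, and reported PFS may be slightly less favourable. Item 1 needs to be in place before patients stop treatment; item 2 can be written at any time before the analysis.
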